#### **4. Change From the Protocol**

No changes in planned analyses were done compared to the protocol.

---

**5. Primary and Secondary Parameters**

AUC0-inf, AUC0-t and Cmax derived from resveratrol, resveratrol-3-glucuronide, resveratrol-4'-glucuronide, and resveratrol-3-sulfate plasma concentrations will be the primary PK parameters. Other PK parameters derived from plasma concentrations (Residual area, Tmax, T1/2 el, CLsys/F (resveratrol only) and Kel) will be secondary PK parameters (refer to Section 10.3).

For urine PK analyses, Ae0-t, Rmax and TRmax parameters will be calculated using urine concentrations (refer to Section 10.4).

Treatment-emergent AEs (TEAEs) will be tabulated by treatment phase. Safety and tolerability data will be reported using descriptive statistics. (refer to Section 9.2).

---

## 6. Analysis Populations

The analysis of safety and tolerability parameters will be based on the study population detailed in Section 6.1. The analysis of PK concentration will be based on the study population detailed in Section 6.2. The analysis of PK parameters will be based on the study population detailed in Section 6.3.

### 6.1 Safety Population

The safety population is defined as all subjects who received at least one dose of the study medication.

### 6.2 Pharmacokinetic Concentration Population

The PK Concentrations (PC) Population will comprise all subjects who received at least one dose of either study drug and have at least one quantifiable PK concentration.

In addition, if a subject has an episode of emesis within 2 hours of study drug administration, their inclusion in the PK Concentration Population will be determined at the discretion of the pharmacokineticist. The PK Concentration Population will be used for the summaries of all PK concentration data.

### 6.3 Pharmacokinetic Parameter Population

The PK population will include all subjects completing at least one period and for whom the PK profile can be adequately characterized.

Any subject with pre-dose concentrations will be excluded from the PK and statistical analysis for the respective analyte for the concerned period if the pre-dose concentration is greater than 5% of the  $C_{max}$  value of that period for that subject.

Data from subjects who experienced emesis during the sampling interval and who were not withdrawn as per criterion established under section 3.7 may be evaluated after completion of the PK analysis. Any subject who experienced emesis within 3h post-dose will be excluded from the statistical analysis. Data (concentrations and PK parameters) from subjects excluded due to a pre-dose concentration greater than 5% of their  $C_{max}$  or from subjects withdrawn due to AEs or vomiting episodes will be presented but excluded from descriptive statistics for the concerned period.

---

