7.5 Dose Escalation Criteria

Each dose level will be dosed sequentially in an ascending fashion, with at least 14 days between dosing of consecutive dose levels. Following completion of each level, safety, tolerability, and PK data will be evaluated by a Safety Committee **and a DSMB** before proceeding to the next dose. The Safety Committee **and the DSMB** will review the whole safety and tolerability data, as well as PK data up to 32 hours post-dose, in order to make decisions regarding progression to the next prescribed dose level, decreasing the next dose level, repeating a dose level or not evaluating any additional dose level, based on consideration of the clinical significance of several safety and tolerability parameters, as well as PK data. The Safety Committee will be composed by at least the Investigator, one medically qualified Sponsor representative, and an independent third party physician. **A formal DSMB will also be established and constituted by an independent group of experts (totally independent of Syneos Health, JOT, and the associated investigators on the study) that advises the NIA Director and the study investigator. The members of the DSMB serve in an individual capacity and provide their expertise and recommendations. The DSMB will be constituted and will act according to the FDA Guidance for Clinical Trial Sponsors - Establishment and Operation of Clinical Trial Data Monitoring Committees¹ and the NIA Guidance on Clinical Trials.²** Dose

escalation may occur only following mutual agreement between the Safety Committee **and the DSMB** members.

Minutes of the safety review committee meeting **and the DSMB** will be prepared and signed by all voting participants. Minutes will include the decision to escalate the dose, confirmation of the next dose level, confirmation of the safety monitoring and washout period, rationale for the decisions and supportive data. The minutes will be shared with the Independent ethics committee (IEC)/Institutional review board (IRB).

Some adjustments to the currently outlined doses may be implemented by the Safety Committee, **or the DSMB** but the dose to be administered at a given dose level will not exceed the dose corresponding to AUC exposures of 2.1 $\mu\text{g}\cdot\text{hr}/\text{mL}$.

Stopping Rules for Dose Escalation

Dose escalation will be halted if any of the events described below occur within one dose level:

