12.2.2 Pharmacokinetic Population

The PK population will include all subjects completing at least one period and for whom the PK profile can be adequately characterized.

Any subject with pre-dose concentrations will be excluded from the PK and statistical analysis for the respective analyte for the concerned period if the pre-dose concentration is greater than 5% of the C_{max} value of that period for that subject.

Data from subjects who experienced emesis during the sampling interval and who were not withdrawn as per criterion established under section 9.11 may be evaluated after completion of the PK analysis. Any subject who experienced emesis within 2 times median T_{max} of the current study (based on the reference product) will be excluded from the statistical analysis. Data (concentrations and PK parameters) from subjects excluded due to a pre-dose concentration greater than 5% of their C_{max} or from subjects withdrawn due to AEs or vomiting episodes will be presented but excluded from descriptive statistics for the concerned period.

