## 7. Interim Analyses

Interim PK analyses will be performed between each dose level and will inform selection of the subsequent dose. The Interim Analyses using PK concentration data will be done after the bioanalytical phase is completed and will include data from subjects who have finalized their study visits at the time of the interim database availability.

PK parameters will be calculated using scheduled sampling times as actual sampling times will not be available for these interim analyses. Only descriptive statistics will be calculated and provided. Interim descriptive analyses of the PK variables will be conducted for each period (Number of observations [N], arithmetic mean, standard deviation [SD], coefficient of variation [%CV], median, minimum [Min], maximum [Max], geometric mean, and %CV geom.mean).

---

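### PK summaries exclude subjects withdrawn for adverse events even when their profile is evaluable, and the interim plan does not say that their values reach the committees choosing the next dose

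*SAP*

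**What the plan says.** SAP 6.3 has separate rules for pre-dose carry-over and for emesis. It then states that concentrations and PK parameters "from subjects withdrawn due to AEs or vomiting episodes will be presented but excluded from descriptive statistics for the concerned period". Protocol 12.2.2 has the same rule: data from subjects "withdrawn due to AEs or vomiting episodes will be presented but excluded from descriptive statistics for the concerned period". The SAP has therefore not departed from the protocol here. Neither text makes an exception for a profile that can be evaluated.

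SAP 7 gives the purpose of the interim: "Interim PK analyses will be performed between each dose level and will inform selection of the subsequent dose". On output it says "Only descriptive statistics will be calculated and provided", and it lists N, arithmetic mean, SD, CV, median, minimum, maximum, geometric mean and its CV. On whose data are used, the interim "will include data from subjects who have finalized their study visits at the time of the interim database availability". It does not name any of the populations in SAP section 6, and it mentions no listing of individual values.

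Under protocol 7.5 the Safety Committee and the DSMB "will review the whole safety and tolerability data, as well as PK data up to 32 hours post-dose". The same section caps the dose by reference to an AUC of 2.1 µg·hr/mL.

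SAP 6.2 defines a PK concentration population of dosed subjects with at least one quantifiable value. Its only qualification concerns early emesis. It adds: "The PK Concentration Population will be used for the summaries of all PK concentration data".

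**The concern.** Leaving a vomited dose out of the summaries is defensible, because drug may have been lost. Withdrawal for an adverse event does not by itself show that a profile is invalid. Profiles that cannot be characterised, carry-over and emesis already have their own rules. What the AE clause adds is the removal of concentrations and parameters that could otherwise be summarised.

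This exclusion may be related to exposure. Protocol 4.3.1 reports that gastrointestinal effects of resveratrol were judged dose-related, so AE withdrawals could come disproportionately from subjects with high exposure. If so, the mean and maximum in the interim summaries would be too low just where they are compared with the AUC limit, and the final summaries for that dose would be low in the same way. The documents do not say whether the limit applies to the mean or to each subject, so both statistics matter.

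**Working it through.** The plan gives no figure on this point. Subject numbers are only judged adequate, so there is nothing to reproduce. The check is a reading of the rules followed by an illustration of size.

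**1. Do the rules combine to remove these subjects?** SAP 6.3 removes AE withdrawals from descriptive statistics. SAP 7 provides descriptive statistics and nothing else. If the 6.3 rule applies at the interim, the interim mean and maximum omit them. SAP 7 does not say whether it applies. Its inclusion phrase does not settle the matter: it could mean visits of the period just completed or, read literally, only subjects who have finished the study.

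**2. Can an AE-withdrawn subject have usable data?** Sampling stops once withdrawal is confirmed (protocol 9.11, SAP 3.7), so a withdrawal during confinement cuts the profile short. Two situations remain:
- The peak may already have been sampled. Median resveratrol Tmax in protocol Table 1 is 0.76 to 1.5 h, although individual values run to 5 h.
- Withdrawal may come late or between periods, for example after the haematology review before a later dose (protocol 9.11). The previous 32-hour profile is then complete, and the rule does not make clear which period is the one concerned.

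**3. SAP 6.2 against 6.3.** The 6.2 population keeps AE withdrawals and is used for every concentration summary. SAP 6.3 excludes their concentrations from descriptive statistics. Both cannot be followed.

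**4. Size.** Inputs:
- n = 24 per Part 1 period (SAP 3.5).
- CV of resveratrol AUCinf from protocol Table 1: 57.2% at 1 g, with a range of 36.2% to 59.1% over 1 to 5 g. These are for unmodified resveratrol, so they are an assumption for JOTROL.
- Number withdrawn, and its link to exposure: not in the documents. Assumed 1 or 2 of 24, under three patterns.

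Model: AUC is lognormal with mean 1 and σ² = ln(1 + CV²). At CV 57.2%, σ² = ln(1.3272) = 0.283 and σ = 0.532. For each of 200,000 simulated sets of 24, the summary without the withdrawn subjects is divided by the summary with all 24.

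| CV | Pattern of withdrawal | Mean ratio, 1 / 2 withdrawn | Maximum ratio, 1 / 2 withdrawn |
|---|---|---|---|
| 57.2% | Unrelated to exposure | 1.000 / 1.000 | 0.992 / 0.984 |
| 57.2% | Probability proportional to exposure | 0.987 / 0.974 | 0.977 / 0.953 |
| 57.2% | Highest exposures (worst case) | 0.934 / 0.887 | 0.805 / 0.705 |
| 36.2% | Probability proportional to exposure | 0.995 / 0.989 | 0.988 / 0.976 |
| 36.2% | Highest exposures | 0.961 / 0.932 | 0.864 / 0.789 |
| 59.1% | Probability proportional to exposure | 0.986 / 0.972 | 0.976 / 0.951 |
| 59.1% | Highest exposures | 0.931 / 0.883 | 0.801 / 0.698 |

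Hand check: at CV 57.2% the expected largest of 24 values is 2.543 times the true mean. Removing it leaves (24 − 2.543)/23 = 0.933, in line with the simulated 0.934.

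On the scale of the limit, a reported mean of 2.1 µg·hr/mL after two withdrawals would correspond to a full-sample mean of:
- 2.1/1.000 = 2.10 if withdrawal is unrelated to exposure;
- 2.1/0.974 = 2.16 if its probability is proportional to exposure;
- 2.1/0.887 = 2.37 in the worst case.

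**The case against.** A reader might infer that these exposures are missing from the information that selects the next dose. The documents do not establish that. The excluding sentence itself says the data will be presented. Protocol section 11 has the samples of AE withdrawals assayed. Protocol 7.5 gives the committees all safety data and PK data to 32 hours, not only summary statistics. In SAP 7, the restriction to descriptive statistics may simply mean that no inferential analysis is done. These points stand. What they do not supply is a commitment that individual values will be shown at the interim, and SAP 7 is the only specification of that output.

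A reader might also infer that an AE-withdrawn subject absorbed the full dose and has valid concentrations. The documents do not say so. The adverse events they stress are gastrointestinal, including diarrhoea, which could alter absorption. Many such profiles will also be truncated, and admitting a truncated AUC would itself pull the summaries down.

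The link from dose-related effects to higher exposure among withdrawals at a single dose is an inference. The cited study compared 1 and 5 g/day over 12 weeks in patients. Finally, escalation does not rest on PK alone: protocol 7.5 halts it after one related serious event, or after related severe events in two subjects. Two AE withdrawals could therefore stop escalation whatever the mean shows.

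These objections limit the size and certainty of any bias. They do not remove the stated exclusion, the silence in SAP 7, or the conflict between SAP 6.2 and 6.3.

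**Conclusion.** The point holds in a limited form and should be fixed. The plan excludes AE-withdrawn subjects from PK descriptive statistics even when their data are evaluable. It does not state the interim population or promise individual values. The interim mean and maximum may therefore omit these subjects; the documents do not show that the committees will be denied the data or that the escalation decision will be biased. The contradiction between SAP 6.2 and 6.3 on concentration summaries stands whatever the bias.

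At CV 57% with 1 or 2 of 24 withdrawn, the mean is unaffected if withdrawal is unrelated to exposure. It falls 1.3% to 2.6% if withdrawal probability is proportional to exposure, and 6.6% to 11.3% in the worst case, where the maximum falls about 20% to 30%. Across the Table 1 CVs, the worst case for two withdrawals is a fall of 6.8% to 11.7% in the mean. All of this rests on an assumed number of withdrawals, lognormal AUCs and CVs from unmodified resveratrol. The effect is small unless withdrawals are concentrated among the highest exposures.

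**What to change.** - **Protocol 12.2.2 and SAP 6.3:** state that AE withdrawal alone does not exclude a period's data. Keep each parameter that is evaluable: Cmax where the peak was sampled, and AUC only where withdrawal did not cut sampling short. Show truncated profiles in listings only. Leave the emesis and pre-dose carry-over exclusions as they are. Say which period is meant when a subject is withdrawn between periods. The requirement to have completed at least one period needs a matching exception, or a Period 1 withdrawal with an evaluable Cmax would still drop out.
- **SAP 7:** replace the statement that the interim "will include data from subjects who have finalized their study visits at the time of the interim database availability" with all subjects dosed in the period just completed. Provide the Safety Committee and the DSMB with individual Cmax and AUC for any AE-withdrawn subject, marking truncated profiles.
- **SAP 6.2:** make the concentration summaries follow the same rule as 6.3.

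The cost is SAP wording, one short interim listing, slightly more variable summaries, and a protocol amendment. The amendment changes more than logistics or administration, so it needs ethics committee approval under protocol 13.1. No further assays are needed, because protocol section 11 already includes these samples.

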## 7. Interim Analyses

Interim PK analyses will be performed between each dose level and will inform selection of the subsequent dose. The Interim Analyses using PK concentration data will be done after the bioanalytical phase is completed and will include data from subjects who have finalized their study visits at the time of the interim database availability.

PK parameters will be calculated using scheduled sampling times as actual sampling times will not be available for these interim analyses. Only descriptive statistics will be calculated and provided. Interim descriptive analyses of the PK variables will be conducted for each period (Number of observations [N], arithmetic mean, standard deviation [SD], coefficient of variation [%CV], median, minimum [Min], maximum [Max], geometric mean, and %CV geom.mean).

---

## **8. Study Population and Exposure**

No inferential analysis will be done. Only observed data will be used.

### **8.1 Subject Disposition**

Subject disposition will be summarized by treatment and overall (frequency and the percentage of subjects). Subject completion and discontinuation information will be listed. In addition, subjects who were dismissed from a period or who did not complete a dosing period will also be presented in this listing, including absence/early discontinuation reason, date and time of discontinuation.

### **8.2 Protocol Deviations**

The protocol deviations will be categorized and listed by subject.

### **8.3 Demographics and Baseline Characteristics**

The descriptive statistics (mean, median, standard deviation [SD], minimum [Min], maximum [Max], and sample size) will be calculated for continuous variables (age, body weight, height and body mass index [BMI]) considering last results (scheduled or unscheduled) obtained at screening. Frequency counts and percentages will be tabulated for categorical variables (age group, sex, ethnicity, and race). Results will be presented summarized by treatment and overall for the safety population and for PK population. All demographic characteristics will be listed by subject.

### **8.4 Medical History**

Medical history at screening will be listed by subject. The Medical Dictionary for Regulatory Activities (MedDRA®), Version 23.1 will be used to classify all medical history findings by System Organ Class (SOC) and Preferred Term (PT).

### **8.5 Prior and Concomitant Medications**

The use of prior and/or concomitant medication will be monitored throughout the study and listed by subject. The World Health Organization Drug Dictionary (WHO DD), Version Sep2020, format B3 will be used to classify all medication reported as from screening through study exit/early termination.

### **8.6 Study Drug Administration**

The study drug administration details (including period, total dose administered, start and end date/time of administration) will be listed by subject for the safety population.

---

## 9. Safety Analyses

Safety data will be evaluated for the safety population through the assessment of AEs, laboratory parameters (hematology, biochemistry, serology, coagulation, urinalysis,), 12-lead electrocardiogram (ECG), physical examination, and vital signs assessments. AEs, laboratory values, and vital signs and ECG will be summarized overall as appropriate. Safety data will be summarized, but will not be subjected to inferential analysis.

Details of the additional laboratory work (RNA-Seq Analysis, Iduronidase, mRNA Frataxin, and Other Possible Tests) will be available in a separate protocol.

Scheduled safety measurements will be repeated according to the clinical site SOPs or upon request from the Investigator or designee. Any abnormal repeated measurement will be evaluated by the Investigator or designee and repeated if judged necessary. Further action may be taken upon the Investigator or designee's request.

### 9.1 Physical Examination Findings

A complete physical examination will be performed at screening. Any abnormal finding prior dosing will be presented in Medical History (MH) and a finding happening after 1st dosing will be categorized as an Adverse Event(AE).

### 9.2 Adverse Events

AEs will be recorded and evaluated for their seriousness, severity, and relationship to the study medication. AEs will be collected and documented during the course of the study and until 4 days following the last study drug administration, if reported. AEs will be followed-up until complete resolution, or until the Investigator judges it to be safe to discontinue follow-up. The relationship to the study medication will be classified according to the clinical site SOPs.

Treatment-emergent AEs and non-TEAEs (those occurring prior to administration of study medication or that first occurred prior to study drug administration and did not worsen in frequency or severity) will be listed. TEAEs will be defined as AEs that occur on or after the date and time of study drug administration, or those that first occur pre-dose but worsen by increase in occurrence or severity after study drug administration. AEs will also be documented if reported.

The incidence of TEAEs will be summarized using the safety population. The MedDRA® dictionary Version 23.1 will be used to classify all AEs reported during the study by SOC and PT.

Incidence of subjects who experienced TEAEs will be presented by treatment and overall, SOC, PT, by Investigator-assessed relationship and also by severity. Each subject may only contribute once to each of the incidence rates, for a TEAE following a given treatment, regardless of the number of occurrences; the highest severity or highest relationship will be presented, as appropriate. In each table, SOC will be presented in descending order of overall incidence rate in terms of frequency of subjects and then in frequency of events (alphabetical order will be used in case of equal rates). For each SOC, PT will be presented the same way.

Incidence of TEAEs (number of events) will also be presented by period(dose) and overall, by SOC, and PT, by Investigator-assessed relationship and severity.

Frequency of subjects experiencing Serious Treatment Emergent Adverse Events and Suspected Unexpected Serious Adverse Drug Reactions; and the number of events would be also summarized per treatment and overall. Also, these events and Serious Adverse Events (SAEs) will be listed per subject.

The assessment of the relationship of an adverse event with the administration of study drug will be classified according to the clinical site SOPs. The relationship of TEAEs will be classified as probably related, possibly related, remotely related and unrelated (not related) to JOTROL.

### 9.3 Laboratory Parameters

Biochemistry will be performed at screening and study exit. The following will be assessed: albumin, alkaline phosphatase (ALP), Aspartate Aminotransferase (AST), Alanine Aminotransferase (ALT), urea, calcium, chloride, glucose, phosphorus, potassium, creatinine, sodium, total bilirubin, and total protein.

Serology will be performed at screening. The following will be assessed: HIV antigen and antibody, hepatitis B surface antigen (HBsAg), and hepatitis C virus (HCV) antibody.

Hematology will be performed at screening, at check-in of study Part 2 (Period 4), and at study exit. The following will be assessed: complete blood count with differential, hemoglobin, and hematocrit.

Coagulation tests will be performed at screening. The following will be assessed: prothrombin time/international normalized ratio (PT/INR) and activated partial thromboplastin time (aPTT).

Urinalysis will be performed at screening and at study exit. The following will be assessed: macroscopic examination, pH, specific gravity, protein, glucose, ketones, bilirubin, occult blood, nitrite, urobilinogen, and leukocytes. Unless otherwise specified, microscopic examination will be performed according to internal procedures.

Hematology, biochemistry, urinalysis, urine pregnancy test, vital signs (blood pressure [BP], respiratory rate [RR], heart rate [HR], and oral temperature [OT]), ECG, and AE monitoring will be performed on the last study day. For subjects who are not included in study Part 2, study exit procedures will be completed after the last blood draw of Period 3 (after 32 hours post-dose on Day 2). For subjects who are included in both study parts, study exit procedures will be completed after the last blood draw of Period 4 (after 32 hours post-dose on Day 2). If not possible, all efforts will be made to complete study exit procedures within 14 days after the last participation of the subject in the study.

A urine pregnancy test will be performed at screening and at study exit, and a serum pregnancy test will be performed at check-in of each period.

A urine drug screen (amphetamines, methamphetamines, barbiturates, benzodiazepines, tetrahydrocannabinol, cocaine, opiates, PCP, MDMA, methadone) and a urine cotinine test will

---

be performed at screening. A urine drug screen, a urine cotinine test, and an alcohol breath test will be performed before dosing at check-in of each period.

Listings of all clinical laboratory results will be provided with the abnormal values flagged with "L" (below normal) and "H" (above normal) for continuous parameters, and "A" (abnormal) for categorical parameters, including the evaluation of the abnormal result as clinically significant or not clinically significant.

Descriptive statistics (mean, median, SD, Min, Max, and sample size) for each clinical laboratory test (continuous variables) will be presented for overall. Change from screening for hematology, biochemistry, and urinalysis will be presented. The unscheduled results will not be included in the summary tables. For categorical variable (urinalysis test), the number of subjects (frequency and percentage) will be tabulated by results (e.g., negative, positive, trace ...). A summary table of shifts from screening to study exit will be provided. Results from repeat tests will not be included in the summary statistics unless the repeat was required (and documented as such) due to technical reasons or an invalid initial result.

For Serology and Coagulation only listing will be provided.

